4.3 Study Details

We plan to recruit 400 patient-partner dyads(800 participants) with diverse backgrounds through the NC Central Cancer Registry rapid case ascertainment (NC CCR RCA). The RCA uses an accelerated process to capture new cases within a week of diagnosis. After receiving a report of localized prostate cancer patients from RCA, we will contact patients' physicians by letter, giving them three weeks to request that a patient not be approached for study inclusion. In one of our studies that RCA facilitated, physicians opted out 81 out of 3400 patients (2.4%) due to patients' severe mental and physical illnesses or insufficient English proficiency. ¹⁰⁸

Study participation data will be provided back to the NC Central Cancer Registry rapid case ascertainment (NC CCR RCA) every six months.

After the 3 week window, we will mail study introduction, a brochure, an opt out letter and informed consent information to potential participants. Then we will call within two weeks to assess interest in participating, answer questions, and screen for eligibility. We will use the same procedure to screen partners' eligibility after eligible patients give permission for us to contact their partner. We will obtain informed consent from eligible patients and partners *via* telephone.

After consented patients and partners independently complete the baseline survey via telephone, dyads will be randomized to PERC or the control group using a 1:1 ratio. v will generate allocation sequences by computerized randomization with randomly permuted blocks of random sizes. The Co-I statistician ([name]) will generate allocation sequences by computerized randomization with randomly permuted blocks of random sizes. *Randomization will be stratified by type of treatment*, surgery or radiation with or without hormonal therapy. Randomization will be centrally allocated using REDCap to ensure the security of randomization lists from all study personnel. After randomization, dyads will be informed of group assignment via email, mailer and/or telephone (the communication

methods participants prefer) and study activities and invited to start either the PERC or NCI program.

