7.0 STATISTICAL CONSIDERATIONS

7.1 Study Design

This study is a two-arm, parallel group randomized controlled trial (RCT) to test the efficacy of PERC, a theory-based, couple-focused, tailored mHealth program aimed to improve the QOL of patients with prostate cancer and their partners. After baseline measures (T1, following consent), 250 patient-partner dyads will be randomly assigned to PERC or to control (usual care plus the NCI website) groups. Participants will complete three surveys to assess the short, intermediate, and long-term effects of PERC: at 4 months post-T1 (T2), 8 months post-T1 (T3), and 12 months post-T1 (T4).

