7.2 Sample Size and Power

We calculated power for comparing our primary outcome (overall QOL) in the Primary Objective using a standard approach for linear mixed models. Because we will assess outcomes for patients and partners separately, we applied a Bonferroni-corrected, two-sided alpha of 0.025 to allow for separate overall tests for patients and partners. This is because, although dyadic data will be modeled simultaneously, conclusions may differ for patients and partners. Based on our pilot test of PERC, we assumed a common standard deviation for the overall QOL scores of 15 points and a within-person correlation between repeated measurements of 0.75. Also, we allowed for losing up to 7% of participants every 4 months, for a total attrition of 20% through 12 months.

Under these assumptions (based on our preliminary studies), we report power for two scenarios, first allowing for attenuating effects, and then assuming constant effects. For the first scenario, we assumed that, on average, PERC would result in improved QOL relative to the control condition, but that these benefits might realistically be expected to decrease somewhat over time. Assuming that the mean difference between groups would be 7.5 points in overall QOL scores at 4 months (i.e., a moderate effect size of 0.5 that would represent a clinically meaningful difference immediately following the intervention) and that this would decrease by 15% every 4 months, randomizing 125 dyads per group would provide 90% power to reject the overall null hypothesis of no differences between groups across all time points. Furthermore, with this scenario, this sample size would provide 94% power for the 4-month comparison, 83% power for the 8-month comparison, and 51% power for the 12-month comparison. For the second scenario, we assumed that the intervention has a constant effect of 6.5 points at each time point (an effect size of 0.43). This sample size will provide at least 80% power for each comparison.

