7.3 Data Analysis Plans

A detailed analysis plan will be developed prior to initiating the study; the following is a summary of the proposed plan. Unless otherwise specified, all analyses will include all randomized participants, in the arm to which they are randomized, regardless of the extent of intervention received (intention-to-treat).

Primary Objective: We will compare the longitudinal mean change in overall QOL between groups using analysis of covariance (ANCOVA), conducted using linear mixed models. Data for patients and partners will be fit together in the same model (accounting for within-dyad correlation), which will allow us to readily assess for differential treatment effects between patients and partners. Mixed models will allow for the inclusion of all observed data for all dyads, assuming any missing data are

missing at random. Each model will include fixed effects (separate for patient or partner) for group, month, group-by-month interactions, the baseline value of the outcome scale, baseline treatment type (surgery and radiation +/-hormonal therapy), number of baseline comorbidities, baseline couple relationship quality, baseline family disruptions, age, race/ethnicity, education, income, and number of people supported by the income. These covariates were selected because they are potentially associated with QOL. Models will include random dyad and participant nested within dyad effects to account for within-dyad and within-person correlations between longitudinal responses. For the primary comparison, separately for each participant type, we will first test for any differences between groups across all 3 time points using an appropriately specified 3 degree of freedom linear contrast. Only if this test is significant ($p \leq 0.025$), will we test for group differences at each time point.

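### The 51% power stated for 12 months does not follow from the stated 15% decay, which gives about 67%; the 90% overall power is not reproduced either (about 86-87%)

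*Combined protocol and SAP*

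**What the plan says.** Section 7.2 bases power on an alpha for each participant type ("we applied a Bonferroni-corrected, two-sided alpha of 0.025"), a "common standard deviation for the overall QOL scores of 15 points", a within-person correlation of 0.75, and 7% loss every 4 months (about 20% by 12 months). Its first scenario starts from a 7.5-point difference at 4 months and says that "this would decrease by 15% every 4 months, randomizing 125 dyads per group would provide 90% power to reject the overall null hypothesis". By visit it reports "94% power for the 4-month comparison, 83% power for the 8-month comparison, and 51% power for the 12-month comparison". Its second scenario, a constant 6.5 points, is credited with at least 80% at each visit.

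Section 7.3 makes the overall test a 3-degree-of-freedom contrast at 0.025. Only if that test is significant, "will we test for group differences at each time point". The model adjusts for "the baseline value of the outcome scale".

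On size, section 7.1 says that "250 patient-partner dyads will be randomly assigned to PERC or to control", which matches 125 per group. Section 4.3 says "We plan to recruit 400 patient-partner dyads", and sections 1.1 and 2.0 also give 400 dyads.

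**The concern.** With 15% decay and modest attrition, power should fall fairly smoothly across visits. The stated figures fall by 11 points from 4 to 8 months and then by 32 points from 8 to 12 months. Effect and attrition change by the same proportions in both intervals, so the second drop looks too steep.

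Hypothesis H1 in section 2.1 names 12 months, and section 7.1 describes that visit as the long-term assessment. The plan presents this comparison as a coin flip. If its own assumptions give about two in three, either the power or the effect behind it is misstated. The overall test gates every visit-specific test, so its power should also be checkable.

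**Working it through.** **Inputs** (section 7.2): n = 125 per group, SD 15, correlation 0.75, two-sided alpha 0.025 (critical value z = 2.2414), 7% loss per 4 months. Retention is 0.930, 0.865 and 0.804, so 116.3, 108.1 and 100.5 per group are seen at the three visits. Compound symmetry is taken from the random dyad and participant effects in section 7.3. Dropout is taken as monotone and all observed data are used, as section 7.3 intends.

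**Effects.** 4 months: 7.5. 8 months: 7.5 × 0.85 = 6.375. 12 months: 7.5 × 0.85² = 5.419. If instead 15% of the initial effect is lost each time, the 12-month value is 7.5 × 0.70 = 5.25.

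**Standard errors of the group difference.** At 4 months, 15 × √(2/116.25) = 1.967. At 8 and 12 months the model borrows from earlier visits of those who drop out; generalised least squares gives 2.000 and 2.027.

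**Power at each visit** = Φ(effect/SE − 2.2414); the opposite tail is negligible.

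| Visit | Effect | Effect/SE | Power | Stated |
|---|---|---|---|---|
| 4 months | 7.5 | 3.812 | 94.2% | 94% |
| 8 months | 6.375 | 3.188 | 82.8% | 83% |
| 12 months | 5.419 | 2.673 | **66.7%** | **51%** |
| 12 months, linear decay | 5.25 | 2.590 | 63.6% | 51% |

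The constant 6.5-point scenario gives 85.6%, 84.4% and 83.3%, in line with the stated minimum of 80%. The method therefore matches every visit-specific figure except the 12-month one.

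**What 51% requires.** Effect = (2.2414 + 0.0251) × 2.027 = 4.60 points. That is 4.595/6.375 = 0.72 of the 8-month effect, a fall of 28% rather than 15%. Three reductions give 7.5 × 0.85³ = 4.61 points, and that effect has 51.2% power. One reduction too many at the last visit is the likely cause, but this is an inference.

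**Other readings of the 12-month figure:**

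| Reading | 15% compounded | Linear |
|---|---|---|
| Only those seen at the visit | 62.6% | 59.5% |
| 80% retained at every visit | 62.3% | 59.2% |
| AR(1) correlation | 65.6% | 62.5% |
| No attrition | 73.1% | 70.0% |

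The range is 59-73%; none reaches 51%. With no attrition the 4- and 8-month figures become 95.7% and 86.8% and no longer match the plan. If the overall test must be passed first, 12-month power is 64.5% (by simulation).

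**Overall 3-degree-of-freedom test.** The noncentrality is δ′C⁻¹δ, where δ holds the three effects and C is the covariance matrix of the three estimated differences. It equals 15.01, and the chi-square critical value is 9.348.

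| 12-month effect | Chi-square | F (198-248 df) |
|---|---|---|
| 5.419 (stated decay) | 86.7% | 85.7-85.9% |
| 5.25 (linear) | 87.0% | 86.1-86.3% |
| 4.606 (one extra reduction) | 89.0% | 88.1-88.3% |
| 5.419, no attrition | 89.5% | 88.7-88.9% |

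The smaller 12-month effect raises overall power because, with correlated visits, a change in the difference over time also counts as evidence against the null.

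**Sample size.** At 200 per group (400 dyads), the stated decay gives 99.5%, 96.3% and 87.3% by visit, and 98.2% overall (chi-square).

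**The case against.** The case for leaving this as minor is a fair one. The 12-month error understates power, so no underpowered comparison is concealed. The SD of 15 takes no credit for the baseline covariate in section 7.3. The plan gives no correlation specifically with baseline, but at assumed values of 0.3, 0.5, 0.6 and 0.75, 12-month power would be 71%, 79%, 85% and 95%, and overall power 90%, 96%, 98% and above 99%. If 400 dyads is the real target, the discrepancy has no design consequence. All of this stands, and it limits the weight of the point; it does not make 51% correct.

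The shortfall in overall power is only 3-4 points and depends on the test chosen. One extra reduction at 12 months would bring it to 88-89%, so a single slip may explain most of both gaps. That is plausible but unproven: under AR(1) the same effect gives only about 86%. Section 7.3 does specify random effects and a 3-degree-of-freedom contrast, but section 7.2 does not say that its 90% used them, or whether the reference distribution was chi-square or F.

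The second scenario gives less comfort than it seems to. Its visit-specific claims hold, but with a constant 6.5 points the overall test that must come first has 79-80% power. The plan claims nothing about that test in this scenario, so this is not an error. The 250-versus-400 conflict is a separate defect; it matters here because it decides which sample size the figures describe.

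**Conclusion.** The concern holds. On the plan's own inputs, 12-month power in the first scenario is about 67% (64% with linear decay), not 51%: a gap of about 16 points, or 13 with linear decay. Confidence is high, because the same calculation matches the plan's other visit-specific figures and no reading of the stated inputs gives 51%.

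Overall power is 86-87%, not 90%. Confidence is moderate, because section 7.2 names neither the covariance structure nor the test statistic. The cause of this smaller gap is not established.

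These results assume 125 dyads per group, monotone dropout at 7% per visit, compound symmetry and no baseline adjustment. They do not show that the trial is too small. They show that the stated decay and the stated 12-month power are incompatible: one implies a difference of about 5.4 points, the other about 4.6.

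**What to change.** - Rerun the calculation for 125 dyads per group. Restate 12-month power as about 67% and overall power as about 86-87%. If a 12-month difference of about 4.6 points was intended, state that decay instead, and note that overall power is then about 88-89%, still short of 90%.
- State the covariance structure and the test (chi-square or F, with degrees of freedom) behind the overall figure.
- Label the figures as unadjusted for baseline and so conservative for the analysis in section 7.3. Baseline-adjusted power over a range of assumed baseline correlations could be added.
- State that the figures refer to 250 dyads, and reconcile sections 7.1 and 7.2 with the 400 dyads in sections 1.1, 2.0 and 4.3.

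The power correction costs one rerun and one edited paragraph. It needs no change to the analysis or to the 125 per group. The restated overall figure is slightly less favourable and the 12-month figure more so. The conflict over the number of dyads needs a decision and edits in the other sections.

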7.3 Data Analysis Plans

A detailed analysis plan will be developed prior to initiating the study; the following is a summary of the proposed plan. Unless otherwise specified, all analyses will include all randomized participants, in the arm to which they are randomized, regardless of the extent of intervention received (intention-to-treat).

Primary Objective: We will compare the longitudinal mean change in overall QOL between groups using analysis of covariance (ANCOVA), conducted using linear mixed models. Data for patients and partners will be fit together in the same model (accounting for within-dyad correlation), which will allow us to readily assess for differential treatment effects between patients and partners. Mixed models will allow for the inclusion of all observed data for all dyads, assuming any missing data are

missing at random. Each model will include fixed effects (separate for patient or partner) for group, month, group-by-month interactions, the baseline value of the outcome scale, baseline treatment type (surgery and radiation +/-hormonal therapy), number of baseline comorbidities, baseline couple relationship quality, baseline family disruptions, age, race/ethnicity, education, income, and number of people supported by the income. These covariates were selected because they are potentially associated with QOL. Models will include random dyad and participant nested within dyad effects to account for within-dyad and within-person correlations between longitudinal responses. For the primary comparison, separately for each participant type, we will first test for any differences between groups across all 3 time points using an appropriately specified 3 degree of freedom linear contrast. Only if this test is significant ($p \leq 0.025$), will we test for group differences at each time point.

Secondary Objectives: We will primarily use similar models to compare each of the QOL subdomains groups, and to test the Secondary outcome hypotheses. We will explore the potential mediating effects of appraisal and coping resources using a longitudinal path analysis model, which will not be the primary analysis for this aim because it requires much stronger assumptions than randomization as a basis for inference. The path model will be a cross-lagged longitudinal model with paths connecting all appraisal and coping variables from prior visits with QOL at subsequent visits, and paths to determine whether a patient's appraisal or coping might influence his partner's QOL, and vice versa. The model will include all appropriate within-dyad and longitudinal correlations. We will assess path model fit using several fit indices: the root mean square error of approximation (RMSEA), along with a 90% confidence interval, Bollen's incremental fit index (IFI), and the Tucker-Lewis fit index (TLI).

Exploratory Objectives: We will test appropriate experimental group-by-characteristic interactions using similar linear mixed models as specified for the Primary Objective. We will only explore effects within subgroups (e.g., within race and ethnicity, high school or lower vs. college or above, higher vs. lower quality relationships, or treatment type subgroups) if the corresponding interaction terms are significant at the 5% level in their respective models. We will also analyze outcome and process data to identify critical characteristics of PERC participants, e.g., differences in racial/ethnic and education, in their PERC use patterns and outcomes (e.g., Forum users vs. non-users).

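### Optional precision gain: the joint patient-partner model in 7.3 could also adjust each person for the other dyad member's baseline FACT-G, which is already collected

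*Combined protocol and SAP*

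**What the plan says.** Under the Primary Objective, section 7.3 puts patients and partners in one model: "Each model will include fixed effects (separate for patient or partner) for group, month, group-by-month interactions, the baseline value of the outcome scale". The list goes on to treatment type, comorbidities, "baseline couple relationship quality, baseline family disruptions" and demographic items. The dyad is otherwise handled through the covariance: "Models will include random dyad and participant nested within dyad effects to account for within-dyad and within-person correlations between longitudinal responses". The other member's baseline FACT-G is not on the list.

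The text does not say that only the person's own baseline enters. It also describes itself as provisional: "A detailed analysis plan will be developed prior to initiating the study; the following is a summary of the proposed plan". No fuller plan is in the documents, so 7.3 is the only specification of the primary model.

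Both baselines are available in time. Section 4.3 says: "After consented patients and partners independently complete the baseline survey via telephone, dyads will be randomized to PERC or the control group". The table in 5.1 has FACT-G at baseline in both arms. Section 7.2 assumes an SD of 15 points and "a within-person correlation between repeated measurements of 0.75". No patient-partner correlation is given anywhere.

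**The concern.** A joint model with a random dyad effect can look as if it already uses everything known about the couple. It does not use the other member's baseline. The dyad effect describes correlation among follow-up responses. Group and month are saturated within each role, so with complete data, and setting the other covariates aside, the role-specific group effect is the difference in follow-up means minus own slope times the difference in own baseline. The other member's baseline has no place in that expression.

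If it predicts a person's follow-up QOL beyond that person's own baseline, the standard errors of the 3-df tests and of the time-point estimates are somewhat larger than the collected data allow. Only precision is at stake.

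**Working it through.** **Inputs.** From 7.2: SD 15, within-person correlation 0.75, two-sided alpha 0.025 per participant type, 125 dyads per group, 7% loss every 4 months (116.3, 108.1 and 100.5 retained per group). Assumed: patient-partner correlation c from 0.2 to 0.5.

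**1. The plan's own power.** A three-visit mixed model with constant correlation 0.75, the stated loss and no baseline adjustment gives standard errors of 1.967, 2.000 and 2.027 points. At effects of 7.5 and 6.375 (7.5 × 0.85), power is 94.2% and 82.8%, matching the stated 94% and 83%. A constant 6.5 points gives 85.6%, 84.4% and 83.3%, in line with the stated minimum of 80% per comparison. So the stated figures take no credit for any baseline adjustment. (The stated 51% at 12 months and 90% overall do not follow from a literal 15% decline, which gives 66.7% and 86.7%. That is a separate matter.)

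**2. Own baseline.** It explains 0.75² = 0.5625 of the variance and leaves 0.4375. The 12-month SE falls from 2.027 to 1.378.

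**3. Both baselines.** Extend the stable dyad and participant components of 7.3 back to baseline. Every patient-partner correlation, same visit or not, then equals c. The other member's baseline has slope (c − 0.75c)/(1 − c²) = 0.25c/(1 − c²), and R² = (0.5625 − 0.5c²)/(1 − c²). The three-visit mean has unadjusted variance (1 + 2 × 0.75)/3 = 0.8333, so its residual is 0.8333 − R², starting from 0.2708.

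| c | Slope | Single-visit residual | Variance cut | SE cut | Three-visit residual | Variance cut |
|---|---|---|---|---|---|---|
| 0.2 | 0.052 | 0.4349 | 0.6% | 0.3% | 0.2682 | 1.0% |
| 0.3 | 0.082 | 0.4313 | 1.4% | 0.7% | 0.2647 | 2.3% |
| 0.4 | 0.119 | 0.4256 | 2.7% | 1.4% | 0.2589 | 4.4% |
| 0.5 | 0.167 | 0.4167 | 4.8% | 2.4% | 0.2500 | 7.7% |

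The 12-month SE goes from 1.378 to 1.369 (c = 0.3) or 1.347 (c = 0.5). On 250 dyads, 250 × (0.4375/residual − 1) is about 1.5 to 12.5 extra dyads for a single visit. The same sum for the three-visit mean gives about 2.4 to 20.8.

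**4. Does the joint fit recover this anyway?** A simulation of the joint model (1,500 replicates, complete data) gave ratios of SE with both baselines to SE with own baseline, averaged over visits, of about 1.00 (c = 0.2), 0.99 (0.3) and 0.97 (0.5). The closed form gives 0.997, 0.993 and 0.976. The joint fit does not recover the gain, and the gain is small.

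**5. Power of the 3-df test** (noncentral chi-square, stated loss, constant effect):

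| True effect | Own baseline | Both, c = 0.3 | Both, c = 0.5 |
|---|---|---|---|
| 3 points | 56.5% | 57.7% | 60.7% |
| 4 points | 85.9% | 86.8% | 88.9% |
| 6.5 points | 99.97% | 99.97% | 99.99% |

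Under the declining scenario power is already 99.98% with own baseline alone.

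**6. How the gain can shrink.** If the correlation between one member's baseline and the other's follow-up is 0.75c rather than c, the slope is (0.75c − 0.75c)/(1 − c²) = 0 and nothing is gained. If shared covariates explained half the dyad component (an assumption), c = 0.3 becomes 0.15/0.85 = 0.176, with within-person correlation 0.60/0.85 = 0.706, and the single-visit cut drops from 1.4% to 0.55%. At c = 0.5 it drops from 4.8% to 2.5%.

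**The case against.** The strongest reply is that this is a preference. Own-baseline ANCOVA with a dyad random effect and a long covariate list is a sound primary analysis. Own baseline already removes 56% of the variance. Relationship quality and income stand in for part of the couple effect. The random effects in 7.3 describe follow-up responses in a model already conditioned on baseline, so carrying that structure back to baseline is an extension. The text is also a summary, so own-only adjustment is an inference. All of this stands, and it is why the point is optional.

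A reader might infer more in three ways, none of which the documents support.

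- *That chance imbalance in one member's baseline biases the other's effect.* It does not. This is ordinary sampling variation, already inside the standard error. Given own-baseline adjustment, its 95% limit is slope × 1.96 × 15 × √(2/125) × √(1 − c²), or about 0.29 points at c = 0.3 and 0.54 at c = 0.5.
- *That the trial loses planned power.* The stated power figures do not rely on this term, and power at the planned effects is close to 100% with own baseline alone.
- *That the plan's own logic requires the term.* The secondary path model does include "paths to determine whether a patient's appraisal or coping might influence his partner's QOL, and vice versa", but that concerns appraisal and coping rather than baseline FACT-G, and 7.3 says it is not the primary analysis for that aim. The reason given for the listed covariates explains the choice made. It is not a rule to include every predictor of QOL.

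What the reply does not remove is that the variable is held on everyone before randomization, that the joint fit does not use it, and that adding it cannot worsen large-sample precision under the specified structure.

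**Conclusion.** The point holds as a low-priority improvement, not as an error. Section 7.3 on its natural reading leaves out the other member's baseline FACT-G. The randomized comparison remains valid without it. Under the dyad-plus-participant structure with c between 0.2 and 0.5, the gain is 0.3% to 2.4% of a single-visit SE. For the 3-df test it is about 1 to 4 power points at c = 0.3 to 0.5 if true effects are 3 to 4 points.

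These sizes rest on an assumed c and on cross-member correlations that do not decay between baseline and follow-up. The documents settle neither. The relative gain does not depend on the number of dyads, so the difference between 400 in sections 1.1, 2.0 and 4.3 and 250 in 7.1 does not affect it.

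**What to change.** In 7.3, before unblinding, replace the single baseline-outcome term with: *the participant's own and the other dyad member's baseline values of the outcome scale (slopes separate for patient and partner)*. Apply it to overall QOL and to the QOL subdomains. If the team prefers to adjust for own baseline alone, the detailed plan should say so, so that the choice is not left open until results are known.

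The cost is one sentence in the plan and one extra slope per role. No new data are needed.

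### Section 7.3 lists a covariance model and baseline slope that do not vary by visit; if QOL correlation falls with time, the 4-month standard error is too large and the 12-month one too small, and a wording change prevents this

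*Combined protocol and SAP*

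**What the plan says.** Section 7.3 (Primary Objective) handles repeated measures through two random intercepts, one for the couple and one for the person inside the couple: "Models will include random dyad and participant nested within dyad effects to account for within-dyad and within-person correlations". The fixed effects, each specific to patient or partner, include "group, month, group-by-month interactions, the baseline value of the outcome scale". No interaction of baseline score with month is listed. Nothing is said about a residual covariance structure, visit-specific variances or robust standard errors.

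For each participant type, a 3-df test across the three follow-ups comes first, at 0.025. Visit comparisons follow only if it is significant, and no level is given for them. The section describes itself as an outline of a fuller plan, which is not among the documents.

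Section 7.2 plans on the same simple structure: "we assumed a common standard deviation for the overall QOL scores of 15 points and a within-person correlation between repeated measurements of 0.75". On multiplicity it says "we applied a Bonferroni-corrected, two-sided alpha of 0.025 to allow for separate overall tests for patients and partners".

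**The concern.** Two random intercepts plus an independent residual amount to compound symmetry over visits. Variance is the same at T2, T3 and T4, and two scores 8 months apart correlate as strongly as two scores 4 months apart. One baseline slope per role also treats baseline as equally predictive at every visit.

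If correlation weakens as the gap widens, baseline explains less at T4 than at T2, so the baseline-adjusted residual variance rises over follow-up. A single pooled variance is then too large at T2 and too small at T4. This concerns visits, not roles: it arises even if patients and partners behave identically.

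At stake are the visit comparisons behind H1 in Section 2.1, which makes claims at all three follow-ups. The T4 comparison carries the durability claim. Section 7.3 reuses similar models for the secondary outcomes and the moderator analyses.

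**Working it through.** **Inputs from the documents.** SD 15 and correlation 0.75; 125 dyads per arm; "losing up to 7% of participants every 4 months, for a total attrition of 20% through 12 months", so retention is 0.93, 0.93² = 0.865 and 0.93³ = 0.804; two-sided 0.025 per role, z = 2.241; "mean difference between groups would be 7.5 points in overall QOL scores at 4 months", falling 15% per 4 months to 6.375 and 5.42; or a constant 6.5.

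**Assumed.** Correlations that fall with the gap, SD still 15, an independent residual, and 2.5% for the visit tests.

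**1. The plan's own figures.** Without baseline adjustment, the T2 SE = √(2 × 225 / (125 × 0.93)) = 1.97 and power = Φ(7.5/1.97 − 2.241) = 94%, as stated. The 8-month 83% also reproduces (82.8%), as does the claim of at least 80% for a constant 6.5 (85.6/84.4/83.3%). The 90% gate power comes out at 86.7% and the 51% at 12 months at 66.7%. Both come close (89.0% and 51.2%) if the 12-month difference is 7.5 × 0.85³ = 4.61. That mismatch is a separate matter.

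**2. Constant correlation 0.75.** Residual variance after baseline adjustment is 1 − 0.75² = 0.4375 of 225 at every visit. The listed model is correct: reported/true SE is 1.00 at each visit and gate size is 2.5%.

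**3. Falling correlation, by hand, ignoring dropout.** With one slope b equal to the mean of the three baseline correlations, the residual variance at visit t is 1 − 2bρₜ + b² (in units of 225), and the model uses their mean. Actual size = 2[1 − Φ(2.241 × √(pooled/true))].

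| ρ at 4/8/12 months | b | Variance T2/T3/T4 | Pooled | Size T2 | Size T4 |
|---|---|---|---|---|---|
| 0.75/0.70/0.65 | 0.70 | 0.44/0.51/0.58 | 0.51 | 1.6% | 3.6% |
| 0.75/0.65/0.55 | 0.65 | 0.4475/0.5775/0.7075 | 0.5775 | 1.1% | 4.3% |
| 0.80/0.70/0.60 | 0.70 | 0.37/0.51/0.65 | 0.51 | 0.8% | 4.7% |

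**4. With dropout (large-sample limit of the listed model).** T2 sizes become 1.6%, 1.1% and 0.9%; T4 sizes become 3.7%, 4.5% and 5.0%. For 0.75/0.65/0.55 the reported SEs are 1.48/1.53/1.56 against true 1.31/1.54/1.75. A REML simulation of the full dyadic model at 0.85/0.75/0.65 (within-couple correlation 0.4 assumed) shows the same pattern: mean reported SEs 1.29/1.32/1.35 against empirical 1.05/1.39/1.56. Without baseline adjustment, decay alone leaves visit SEs within 1%, so the distortion comes through the baseline adjustment.

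**5. The gate.** The T4 sizes above are ungated. Under the global null, requiring the gate first brings T4 rejection to 1.8% for 0.75/0.65/0.55, and to about 1–2% across the scenarios. The gate's own size is about 2.7–3.2% in the three scenarios and 3.5% under AR(1) 0.75, against 2.5%.

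**6. Gate power, listed model against unstructured covariance with baseline-by-month.**

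| Effect | ρ | Listed | Unstructured |
|---|---|---|---|
| Planned, fading | 0.75/0.65/0.55 | 99.8% | 99.9% |
| Constant 6.5 | 0.75/0.65/0.55 | 99.4% | 99.6% |
| Constant 6.5 | AR(1) 0.75 | 98.3% | 99.3% |
| Half the planned fading effect | 0.75/0.65/0.55 | 51% | 60% |
| Half the planned fading effect | 0.75/0.70/0.65 | 59% | 63% |
| Delayed, 0/2.5/5 points | 0.75/0.65/0.55 | 78% | 67% |

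The largest loss found at a planned effect was 1.3 points, under AR(1) 0.60. Planned-effect power is higher here than in Section 7.2 because these runs adjust for baseline.

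**The case against.** **The text does not force this model.** Section 7.3 names random effects but is silent on the residual, and a structured residual could sit beside them. This stands, which is why the point is conditional on the usual independent residual. The silence still leaves the covariance unspecified in the only plan available.

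**Nothing in the documents shows decay.** Section 7.2 gives one correlation from pilot work, and under it the listed model is exactly right. This also stands. A reader might infer that the visit error bars are wrong as planned; the documents do not support that. Even under decay, the T3 standard error is right to within about 1% in the main scenario (1.53 against 1.54).

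**The gate protects T4.** It does under the global null. It does not when a real early effect opens the gate and the 12-month effect is absent, which is the case a durability claim must survive.

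**The primary test loses power.** A reader might infer this stronger consequence. It fails as a general statement: at the planned effects the change is negligible, a loss appears only for smaller fading or flat effects, and the sign reverses for a delayed effect. Half the planned effect is not a size the documents plan for.

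**The remedy is one of several.** Structured residuals or robust standard errors would also repair the error bars. Agreed; the need is to prespecify one.

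**Conclusion.** The point holds in conditional form and is a cheap improvement, not a threat to the primary conclusion at the planned effects. If correlation declines as assumed, the T2 test is conservative, the T4 test runs at roughly one and a half to two times an assumed 2.5% level once an earlier effect has opened the gate, and the 3-df gate is mildly anti-conservative. If correlation is constant at 0.75, nothing is wrong and nothing is lost by changing.

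The sizes rest on assumed correlations, a constant SD, an independent residual and the assumed visit-test level. SE ratios and test sizes do not depend on the number of dyads, so they are unaffected by the difference between 400 dyads (Sections 1.1, 2.0 and 4.3) and 250 (Section 7.1). The power figures use 125 per arm.

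**What to change.** In Section 7.3, before outcomes are examined by arm:

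- Replace the two random intercepts with an unstructured covariance over role and visit within dyad (6 × 6), using Kenward-Roger degrees of freedom.
- Let the baseline QOL slope vary by month as well as by role.
- Name the fallback if the model does not converge: heterogeneous Toeplitz by role, then the listed model with dyad-clustered robust standard errors.
- State the level for the visit comparisons.

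The cost is wording, plus 6 × 7 / 2 = 21 covariance parameters in place of 3. With 250 dyads these should be estimable, and the fallback covers the small convergence risk. For a delayed effect, the corrected gate would reject less often than the listed one.
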